#### **4.1.4.4 Time to minimal symptoms based on TEQ**

Time to minimal symptoms (based on the TEQ) will be defined as the first time at which the response to Question 3 of the TEQ is 'Yes'.

- Patients who do not have minimal symptoms during the time that they are followed-up will be censored at the last time at which the TEQ is recorded. Note: If a patient was randomized but did not have any post-baseline efficacy data then they will be censored at Presentation.
- The time to minimal symptoms for patients who receive disallowed concomitant medication will be censored at the last time at which the patient had an Overall VAS score prior to their receipt of disallowed concomitant medication. If this is Presentation and hence prior to study drug administration then the time to minimal symptoms will be censored at time 0 minutes.

Time to minimal symptoms (minutes) will be calculated as:

Actual date and time of minimal symptoms (or date and time of censoring) – Date and time of first Study Drug Admin

The actual date and time of minimal symptoms will be used in the calculation.

#### **4.1.4.5 Time to complete resolution**

In a diary, dispensed at discharge from the hospital, the patient will be asked to record the date and time at which all angioedema symptoms at all locations have resolved (complete resolution). If needed, depending on the patient's level of understanding, parents may assist in completion. During the Day 28 follow-up visit, the date and time of complete resolution of symptoms, as reported by the patient in the diary, is then recorded in the Day 28 CRF.

Time to complete resolution of all symptoms at all locations will be assessed using the answer recorded on the CRF.

- Time to complete resolution of symptoms will be defined as 'Time HAE attack resolved' on the CRF.
- Patients who do not have complete resolution of symptoms during the time that they are followed-up will be censored at 72 hours if the patient confirms that they did not have complete resolution of symptoms during the follow-up time, or at the time of discharge if the 'Date HAE attack resolved' and 'Time HAE attack resolved' on the CRF were not completed. 72 hours is chosen as this is the average length of time that swelling would be expected to subside without treatment. Note: If a patient was randomized but did not have any post-baseline efficacy data then they will be censored at Presentation.
- The time to complete resolution of symptoms for patients who receive disallowed concomitant medication will be censored at the last time the patient had an Overall VAS

score prior to their receipt of disallowed concomitant medication. If this is Presentation and hence prior to study drug administration then the time to complete resolution of symptoms will be censored at time 0 minutes.

Time to complete resolution of symptoms (minutes) will be calculated as:

Actual date and time of complete resolution of symptoms (or date and time of censoring) –  
Date and time of Study Drug Admin

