The patient should be observed for 4 hours in the hospital. After 4 hours, the investigator may decide to discharge the patient from the hospital if the patient's condition is judged well enough. The investigator may consult the VAS-scores to verify if Time to Beginning of Relief has been

achieved. If the patient's condition is not well enough, the patient will remain in the hospital under the appropriate medical care.

At hospital discharge

- perform physical examination
- Dispensation of diary, in which patients will be instructed to record any changes in their health condition and concomitant treatments following the study medication administration. Also, the time at which there is complete resolution of the angioedema attack symptoms has to be indicated
- Dispensation of additional VAS and TEQ questionnaires. The patients will be instructed to continue completing the VAS-score and TEQ at T8h (\pm 1 hour) and T24h (\pm 4 hour) (i.e. at the time of the phone call). The 8 hour time point may be facilitated by a study coordinators phone call.

The diary and questionnaires (VAS and TEQ) are to be returned on the visit at Day 28. If patients report, or if legal guardians notice, deterioration of HAE symptoms, the investigator should be contacted immediately.

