10.2.4.3 Follow-up Visits

At 24 hours (\pm 4h) following treatment administration, a phone call is made to the patient in order to:

- assess HAE symptoms (registering localization, severity and time course) in order to document the further evolution of the acute attack (resolution, exacerbation, late relapse etc), including patient's VAS score and TEQ
- remind about detailed completion of the diary for AEs, concomitant medication
- ask patient if complete resolution of symptoms has occurred, and if so record the exact date and time in the CRF
- record and assess new AE/SAE's or changes to ongoing AE/SAE's since the last infusion
- record changes in concomitant medication and/or need for rescue medication

On Day 28 (\pm 3 days) following treatment administration, a center visit is scheduled, at which the following procedures are scheduled:

- return of the diary including recording of time of complete resolution of symptoms
- perform routine physical examination
- blood sampling for Immunological Analysis and routine laboratory safety parameters
- assess HAE history during preceding 28 days (e.g. occurrence of intercurrent HAE-episodes etc)
- evaluate diary and record and assess new AE/SAE's or changes to ongoing AE/SAE's since the last infusion

Safety of Ruconest in 2-13 year old HAE patients

- evaluate diary and record changes in concomitant medication and/or need for rescue medication

On Day 90 (\pm 7 days) following treatment administration, a center visit is scheduled, at which the following procedures are scheduled:

- perform routine physical examination
- record vital signs (supine blood pressure, pulse, body temperature)
- blood sampling for Immunological Analysis
- HAE history since previous treatment (e.g. occurrence of intercurrent HAE-episodes etc).
- record and assess new AE/SAE's or changes to ongoing AE/SAE's since the last infusion
- record changes in concomitant medication and/or need for rescue medication

Day 28 and Day 90 visits will occur following an occasion treated with Ruconest. If a new attack is treated before completing the follow-up visits for the previous attack, the D28 or D90 visit schedule will be reset based on the most recent treatment. In that case, the diary is to be returned and evaluated at the time the patient presents in the clinic with the new attack.

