Time to the beginning of relief based on patient's VAS scores; time lapsed from the beginning of the infusion of study medication to the beginning of an effect. This variable will be based on the overall VAS for each eligible location. Time to beginning of relief is defined as the first time point at which the "overall severity VAS" decreases by at least 20 mm with persistence of the decrease at the next assessment time so that for the next value at the location a decrease of at least 20 mm with respect to baseline is also observed. Time to beginning of relief will also be calculated based on the IS and Questions 1 and 2 of the TEQ.

Time to minimal symptoms:

Time to minimal symptoms based on patient's VAS scores; time from the start of the infusion of study medication to the first assessment time at which the overall severity VAS reaches a value of less than 20 mm for all locations. Time to minimal symptoms will also be calculated based on the IS and Question 3 of the TEQ.

Time to complete resolution:

Time to complete resolution based on the time, as indicated by the patient in the diary, at which all angioedema symptoms are fully resolved at all locations.

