**Attachment 1 List of Tables, Listings and Figures**

Table Number	Title	Analysis Set	Repeat
Table 14.1.1.1	Summary of Patient Disposition	Screening	Unique
Table 14.1.1.2	Summary of Patient Disposition	ITT	Repeat of 14.1.1.1
Table 14.1.2	Summary of Analysis Sets	All patients	Unique
Table 14.1.3	Summary of Protocol Violations	Safety	Unique
Table 14.1.4.1	Summary of Demographics and Baseline Patient Characteristics	Screening	Unique
Table 14.1.4.2	Summary of Demographics and Baseline Patient Characteristics	Safety	Repeat of 14.1.4.1
Table 14.1.4.3	Summary of Demographics and Baseline Patient Characteristics	ITT	Repeat of 14.1.4.1
Table 14.1.4.4	Summary of Demographics and Baseline Patient Characteristics	PP	Repeat of 14.1.4.1
Table 14.1.5	Summary of Medical History	Safety	Unique
Table 14.1.6	Summary of Relevant HAE History	Safety	Unique
Table 14.1.7	Summary of Relevant HAE Attack History	Safety	Unique
Table 14.1.8	Summary of Concomitant Medication	Safety	Unique
Table 14.2.1.1.1	Summary of Overall VAS Score by Time and Attack	ITT	Unique
Table 14.2.1.1.2	Summary of Overall VAS Score by Time and Attack	PP	Repeat of 14.2.1.1.1
Table 14.2.1.2.1	Summary of Change in Overall VAS Score from Baseline by Time and Attack	ITT	Repeat of 14.2.1.1.1
Table 14.2.1.2.2	Summary of Change in Overall VAS Score from Baseline in VAS by Time and Attack	PP	Repeat of 14.2.1.1.1
Table 14.2.1.3.1	Summary of TEQ by Time and Attack	ITT	Unique
Table 14.2.1.3.2	Summary of TEQ by Time and Attack	PP	Repeat of 14.2.1.3.1
Table 14.2.1.4.1	Summary of Investigator Symptom Score by Time and Attack	ITT	Unique
Table 14.2.1.4.2	Summary of Investigator Symptom Score by Time and Attack	PP	Repeat of 14.2.1.4.1
Table 14.2.1.5.1	Time to Beginning of Relief (VAS, IS and TEQ)	ITT	Unique
Table 14.2.1.5.2	Time to Beginning of Relief (VAS, IS and TEQ)	PP	Repeat of 14.2.1.5.1
Table 14.2.1.6.1	Time to Minimal Symptoms (VAS, IS and TEQ)	ITT	Repeat of 14.2.1.5.1
Table 14.2.1.6.2	Time to Minimal Symptoms (VAS, IS and TEQ)	PP	Repeat of 14.2.1.5.1
Table 14.2.1.7.1	Time to Complete Resolution (Diary)	ITT	Repeat of 14.2.1.5.1
Table 14.2.1.7.2	Time to Complete Resolution (Diary)	PP	Repeat of 14.2.1.5.1
Table 14.2.1.8.1	Summary of Therapeutic Failure	ITT	Unique
Table 14.2.1.8.2	Summary of Therapeutic Failure	PP	Repeat of 14.2.1.8.1
Table 14.2.1.9	Receipt of a Second Dose of rhC1INH	ITT	Unique
Table 14.2.2.1.1	Functional C1INH (% of Normal) Over Time	PK/PD Concentration Set	Unique

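### SAP 4.1.4.5 censors complete resolution at discharge when the CRF resolution fields are blank and does not name the 24-hour call as a source

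*SAP*

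**What the plan says.** SAP 4.1.4.5 has the patient record the resolution time in a diary handed out at discharge. That time, "as reported by the patient in the diary, is then recorded in the Day 28 CRF", is the one analysed. Protocol Appendix F gives the same source ("Time to complete resolution based on the time, as indicated by the patient in the diary"), and the SAP's output list labels the corresponding tables as diary-based.

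For attacks without a resolution time, SAP 4.1.4.5 has two main branches. One covers confirmed non-resolution, where the patient "will be censored at 72 hours if the patient confirms that they did not have complete resolution of symptoms during the follow-up time". The second covers blank CRF fields and sets a different censoring point: "or at the time of discharge if the 'Date HAE attack resolved' and 'Time HAE attack resolved' on the CRF were not completed". Use of disallowed medication has a separate censoring rule that is not at issue here.

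Protocol 10.2.4.2 gives a usual stay of 4-5 hours: "After 4 hours, the investigator may decide to discharge the patient from the hospital". Protocol 10.2.4.3 then schedules a telephone call at 24 hours (plus or minus 4), at which staff must "ask patient if complete resolution of symptoms has occurred, and if so record the exact date and time in the CRF". SAP 4.1.4.5 does not mention this call.

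Two general SAP rules also bear on the endpoint. Section 6.7.4 censors non-events at the last available assessment of the endpoint concerned. Section 5.5.1 assumes no event where the data are insufficient to tell.

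**The concern.** The diary is handed out at discharge. An attack with blank resolution fields is therefore censored just as diary follow-up begins, although the protocol collects the status of this same endpoint about 20 hours later. Two kinds of information are at risk:

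- **Event times.** A resolution reported at the call may never reach the analysis.
- **Event-free time.** A child reported as still symptomatic at the call may leave the risk set at discharge.

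Kaplan-Meier estimation treats censored attacks as if they would go on to resolve like those still under observation. If blank records are mainly slow or mainly fast resolvers, the curve is biased, and the call data that would correct it are left out. With about 20 treated patients and a separate analysis for each attack number, a few blank records can move the estimates.

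**Working it through.** There is no planned figure to reproduce: the SAP tests no hypothesis and the sample size was not formally calculated. The check has three parts.

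**1. Time lost or added per blank record.** Inputs: discharge at 4-5 h and the call at 24 h, window 20-28 h (Protocol 10.2.4.2 and 10.2.4.3); confirmed non-resolution censored at 72 h (SAP 4.1.4.5).

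- If the child is censored at discharge, observed time lost = call time minus discharge time. Nominal 24 - 4 = 20 h; shortest 20 - 5 = 15 h; longest 28 - 4 = 24 h.
- If a not-resolved answer at the call counts as confirmation, unobserved time added = 72 minus call time. Nominal 72 - 24 = 48 h; range 72 - 28 = 44 h to 72 - 20 = 52 h.

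Neither branch censors where observation stops. SAP 6.7.4, read literally, would: for a family reached by telephone, the last assessment of this endpoint is the call. SAP 5.5.1 assumes no event only where data are insufficient, and a resolution time taken at the call is sufficient.

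**2. An example by hand (assumed data).** Take 20 attacks: 16 with resolution times evenly spaced from 6 to 60 h (step 54/15 = 3.6 h) and 4 blank. Six of the 16 resolve by 24 h (6, 9.6, 13.2, 16.8, 20.4 and 24 h).

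- Discharge rule: the 4 blanks leave at 4 h, before any event. Resolved by 24 h = 6/16 = 37.5%.
- Call used, all 4 unresolved at 24 h: 6/20 = 30%.
- Call used, all 4 resolved between 4 and 24 h: (6 + 4)/20 = 50%.

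The discharge rule gives 37.5% in both cases because it cannot tell them apart. The call can.

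**3. Simulation.** Assumptions not in the documents: 20 patients, log-normal resolution time with SD of the log 0.8, true median 6, 12 or 24 h, up to 2, 4 or 6 blanks (fewer when a run had fewer eligible patients), 2,000 runs per setting. The discharge rule censors blanks at 4 h. The alternative uses the event time if it is at or before 24 h and otherwise censors at 24 h. Results for a 12 h median and up to 4 blanks:

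| Who is blank | Resolved by 24 h, discharge rule | Resolved by 24 h, using the call |
|---|---|---|
| Unresolved at 24 h | 96% | 81% |
| Resolved between 4 and 24 h | 75% | 81% |
| Random among those unresolved at 4 h | 80% (SD 0.101) | 80% (SD 0.091) |

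Over all settings, the discharge rule overstated the 24-hour proportion by 3.8 points (99.6% against 95.8%) to 21.1 points (71.1% against 50.0%) when the blanks were non-resolvers. It understated it by 0.7 points (95.2% against 95.9%) to 21.5 points (28.7% against 50.2%) when they were resolvers. Using the call reproduced the full-data 24-hour estimate in every setting. I rely on the 24-hour proportion rather than the median because at this sample size the Kaplan-Meier median is sensitive to step convention: it moved from 11.4 to 12.3 h even with random blanks.

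**The case against.** The strongest reply is that the trigger is a blank CRF field, not a blank diary. The protocol also sends the call's date and time to the CRF, and the CRF layout is not in the documents. If both entries share one field, a resolution reported at the call is kept. The censoring sentence is also addressed to patients without resolution during follow-up, and a child with a documented resolution is not plainly one of them. This stands as a limit: loss of reported resolutions is possible, not shown. It does not help the child reported unresolved at the call, who still goes to discharge or to 72 hours.

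It can also be said that the SAP follows the protocol's diary definition. It does, and the diary should stay the first source. That does not justify censoring before the last time the child's status was known.

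A reader might infer two stronger things:

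- **That the loss falls on children with frequent attacks, because a new attack resets the Day 28 visit.** The documents provide for this. Protocol 10.2.4.3 has the diary returned and evaluated when the new attack presents, and SAP 2.2 uses it to complete part of the Day 28 CRF for the previous attack.
- **That the rule flatters the product.** It does so only if the blanks are mainly non-resolvers; the sign reverses if they are resolvers.

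**Conclusion.** The point holds as a defect in the censoring rule. SAP 4.1.4.5 does not use the 24-hour call, and it conflicts with SAP 6.7.4 and with the sense of 5.5.1. For a child reported unresolved at the call, it either loses 15-24 h of observed time or adds about 48 h that nobody observed. Reported resolutions are lost as well, unless the call and Day 28 entries share a CRF field.

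The effect on the estimates is uncertain in sign and size. It depends on how many fields are blank and for whom, and the documents give neither. The percentages above illustrate what could happen under stated assumptions; they are not estimates for this trial. If blanks are random, the cost is precision only. The 4-5 h discharge time is the usual stay; a child kept longer is censored later and loses less.

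Time to complete resolution is an exploratory, descriptive endpoint in a study whose primary objective is safety. Priority is low to moderate.

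**What to change.** Replace the two main censoring branches of SAP 4.1.4.5 with one ordered rule:

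1. Use the diary resolution time where it exists.
2. If it is blank, use the date and time recorded at the 24-hour call.
3. If neither gives a resolution, censor at the last contact at which non-resolution was documented, normally the 24-hour call.
4. Use discharge only if there was no later contact.

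State whether the call and Day 28 entries share a CRF field, and bring sections 4.1.4.5, 5.5.1 and 6.7.4 into line. Report how many attacks had blank fields and which source supplied each resolution time.

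The cost is SAP wording and use of data the protocol already requires. The small downside is a departure from the diary-only definition in Protocol Appendix F, which should be stated, and the table titles would change. The SOP deviation form attached to the SAP records the analysis as finalised, so the practical route now is a described and justified change, or a sensitivity analysis, in the clinical study report. SAP 7.5 provides for changes made after database lock to be reported there.

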#### **4.1.4.6 Therapeutic failure**

A patient will be assessed as having had a therapeutic failure if any of the following occurs:

- Time to the beginning of relief of symptoms for the attack based on the Overall VAS occurs later than 4 hours after Baseline.
- Within 4 hours after beginning of treatment administration and after beginning of relief, the Overall VAS increases again to a value of at least the Baseline score.
- The patient has occurrence of HAE at a new location within 4 hours after achieving beginning of relief of symptoms (Based on an IS score of greater than 0 at a new location that had an IS score of 0 at Baseline). Beginning of relief of symptoms here is based on the Overall VAS as defined in Section 4.1.2.1.
- The patient taking any of the medications that may interfere with the assessment of the impact of Ruconest on efficacy measures, between the onset of the attack and prior to time of initial relief of symptoms including:
  - Narcotics
  - Plasma-derived C1 inhibitor
  - Fresh frozen plasma
  - Bradykinin receptor antagonist
  - Analgesics
  - Anti-emetics
  - Non Steroidal Anti-Inflammatory Drugs (NSAIDs)
  - Paracetamol (within 45 minutes before the administration of Ruconest)

The medical monitor will perform a manual review of the concomitant medications and identify those which fall into the above categories.

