10.1.2 Secondary study parameters

At the first attack, pharmacokinetic and pharmacodynamic parameters will be evaluated for:

- C1INH activity and C4.

The following parameters will be determined: baseline level; C_{max} ; dose-normalized C_{max} ; T_{max} ; AUC above baseline; dose-normalized AUC; clearance; volume of distribution; elimination half-life ($t_{1/2}$); V_{max} ; K_m .

Efficacy will be evaluated by

- time to beginning of relief assessed by using the overall severity VAS, defined as the first time point with a decrease of at least 20 mm with respect to baseline at any eligible location, with persistence at the next time point (see section [10.2.3](#))
- time to minimal symptoms assessed by using the overall severity VAS, defined as the first time point at which the overall severity VAS falls below 20 mm for each assessed location
- time to beginning of relief assessed by using the IS-score defined as the first time point with a decrease of at least 1 point on the IS-score (investigator assessment) compared to baseline, at any eligible location.
- time to minimal symptoms assessed by using the IS-score, defined as the first time point at which the IS-score is less than or equal to 1 point for all assessed locations

All terms are defined in the List of Definitions in [Appendix F](#). See [section 10.2.3](#) for a detailed description of these efficacy parameters.

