10.1.3 Other study parameters

Safety variables after single and repeat treatment that will be subject to exploratory analysis:

- vital signs
- ECG
- Routine clinical laboratory parameters

Efficacy variables that will be subject to exploratory analysis:

- time to beginning of relief based on questions 1 and 2 of the TEQ, defined as the first time-point at which Question 1 is answered as a little better, better or much better and Question 2

Safety of Ruconest in 2-13 year old HAE patients

is answered as yes for the most severe eligible location, with persistence of these responses at the next time point.

- time to minimal symptoms on the basis of Question 3 of the TEQ, defined as the first time-point at which Question 3 is answered as yes for all locations
- time to complete resolution based on the time-point at which all symptoms at all locations have resolved
- therapeutic failure: A patient will be assessed as having had a therapeutic failure if any of the following occurs:
 - time to the beginning of relief of symptoms for the attack based on the overall VAS occurs later than 4 hours after baseline
 - within 4 hours after beginning of treatment administration and after beginning of relief the overall VAS increases again to a value of at least the baseline score
 - the patient has occurrence of HAE at a new location within 4 hours after achieving beginning of relief of symptoms
 - the patient taking any of the medications that may interfere with the assessment of the impact of Ruconest on efficacy measures, between the onset of the attack and prior to time of initial relief of symptoms including:
 - Narcotics
 - plasma-derived C1 inhibitor
 - Fresh frozen plasma
 - Bradykinin receptor antagonist
 - Analgesics
 - Anti-emetics
 - Non Steroidal Anti-Inflammatory Drugs (NSAIDs)

Any change in current and optional maintenance therapy (androgens and/or anti-fibrinolytics) from the time of the onset of the current attack is not allowed. The dosage of androgens and anti-fibrinolytics may not be increased earlier than 24 hours after the treatment with study medication.

For a detailed description and definition of used terms, see [Appendix F](#).

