Acute angioedema attack at a new location will be identified as an IS score greater than 0 at any time up to (and including) 24 hours for a location that had an IS score of 0 (or missing IS score) at Baseline.

Peripheral edema:

Safety of Ruconest in 2-13 year old HAE patients

Angioedema at peripheral localizations (occurring in subcutaneous rather than submucosal tissue), i.e. not localized in the abdomen (gastrointestinal tract) and/or in the facial-oro-pharyngeal region and/or in the urogenital region ('submucosal' sites), e.g. swelling at extremities, hand, wrist, lower arm, upper arm, foot, leg, ear, chest wall, abdominal wall, neck, buttocks.

Early relapse:

Beginning of relief of symptoms by overall VAS within four hours, followed by an increase of VAS score to baseline value or higher, within the first 8 hours after baseline.

Late relapse:

Beginning of relief of symptoms by overall VAS within four hours, followed by an increase of VAS value to baseline value or higher, more than 8 hours after baseline and at most 24 hours after baseline.

Spontaneous regression:

Decrease in symptoms of angioedema scored with investigator score at $t = 0$ h compared with score at the time of initial evaluation by 1 or more at an eligible location.

Submucosal attack:

Attack with presumed or visible involvement of submucosal tissue at any of the possible eligible sites, i.e. localized in the abdomen (gastrointestinal tract), facial-oro-pharyngeal region, larynx, and/or urogenital region.

Therapeutic failure:

Time to the beginning of relief based on the VAS later than 4 hrs after study medication administration, relapse of the attack within 4 hrs, and/or occurrence of HAE at a new location within 4 hours after achieving beginning of relief of symptoms. The episode will also be considered a failure if the patient recorded taking medications that may have interfered with the assessment of the impact of Ruconest on efficacy measures, prior to time of initial relief of symptoms including: narcotics, plasma-derived C1 inhibitor, recombinant human C1 inhibitor, fresh frozen plasma (FFP), or anti-emetics.

Time to beginning of relief:

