## **4.1.2 Primary Efficacy Measure**

### **4.1.2.1 Time to beginning of relief based on Overall VAS**

The time to beginning of relief will be assessed using the Overall VAS score, where time of beginning of relief will be assessed as the first time point at which the VAS score decreases by at least 20mm at any eligible anatomical location compared to Baseline, with persistence of the decrease at the next time point.

The time of relief will be the first time point at which the Overall VAS score decreases by at least 20mm compared to Baseline. For example, if this was achieved at 2 hours with persistence shown at 4 hours then the time of beginning of relief of symptoms will be 2 hours.

Patients who do not have beginning of relief during the time that they are followed-up will be censored at the last time at which the Overall VAS score is recorded at any eligible anatomical location. Note: If a patient was randomized but did not have any post-baseline efficacy data then they will be censored at Presentation. Patients who first have a decrease of  $\geq 20$ mm at the last time Overall VAS score was recorded will not have achieved beginning of relief with persistence. Therefore, they will be censored at the penultimate time that Overall VAS was recorded.

Time to beginning of relief (minutes) will be calculated as:

Actual date and time of first relief (or date and time of censoring) – Date and time of the Baseline Overall VAS assessment

The actual date and time of beginning of relief will be used in the calculation.

The beginning of relief assessed using Overall VAS will be assessed for the first eligible location at which time to beginning of relief of symptoms by Overall VAS first occurred. Only locations with a populated start date and time and corresponding Overall VAS will be used for the calculation of time to beginning of relief.

For the evaluation of persistence, the decrease of  $\geq 20$ mm is required at the next assessment time for which the Overall VAS score is not missing. For example, if 2 Overall VAS determinations with  $\geq 20$ mm decline from Baseline are separated by a missing scheduled assessment then beginning of relief with persistence would have still been achieved.

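### Therapeutic failure and VAS/IS time to event are defined inconsistently: the new-location rule, the medication list and time zero differ between the SAP and parts of the protocol

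*SAP*

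**What the plan says.** **New location.** Protocol Appendix F treats a location as new if its IS rises above 0 after being 0 or missing at Baseline. The third bullet of SAP 4.1.4.6 requires a Baseline IS of 0 and does not mention missing scores.

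**Interfering medication before relief.** Protocol 10.1.3 lists seven classes. SAP 4.1.4.6 lists the same seven plus paracetamol within 45 minutes before dosing. Appendix F lists five, one of which is recombinant human C1 inhibitor. Protocol 8.2.2 says additional treatment makes the attack a failure, but excepts Ruconest.

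**Time zero.** SAP 4.1.4.6 has "Time to the beginning of relief of symptoms for the attack based on the Overall VAS occurs later than 4 hours after Baseline", and Protocol 10.1.3 has "time to the beginning of relief of symptoms for the attack based on the overall VAS occurs later than 4 hours after baseline". Appendix F has "Time to the beginning of relief based on the VAS later than 4 hrs after study medication administration", and defines VAS time to beginning of relief as "time lapsed from the beginning of the infusion of study medication to the beginning of an effect". SAP 4.1.2.1 instead subtracts the "Date and time of the Baseline Overall VAS assessment", and SAP 4.1.4.1 does the same with the Baseline IS. The SAP's TEQ and complete-resolution endpoints (4.1.4.3 to 4.1.4.5) count from study drug administration.

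**Status of Appendix F.** Protocol 10.1.2 states "All terms are defined in the List of Definitions" in that appendix, and Protocol 10.1.3 sends the reader there too ("For a detailed description and definition of used terms, see").

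**The concern.** The same attack can be a failure under one passage and not under another. The deciding fact may be a box left blank rather than marked 0 at Baseline, a second Ruconest dose given before relief, or a few minutes between the Baseline VAS and the infusion. A reader of the report could not tell which rule produced the failure percentage, the table of reasons, or the first- and last-attack bar charts.

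The clock difference also puts unlike quantities in one table. Table 14.2.1.5 shows time to beginning of relief by VAS, IS and TEQ, the first two counted from a pre-dose assessment and the third from dosing. Table 14.2.1.6 has the same mix for time to minimal symptoms.

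SAP 7.1 lists changes from the protocol and names only the reduced set of PK parameters. The SAP's time-to-event origin and its new-location rule are therefore undeclared departures from Appendix F.

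**Working it through.** The documents give no failure rate, so there is no planned figure to reproduce.

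**1. New location**
- Protocol 10.2.3 has the investigator score IS at each affected location, so an unaffected location may have no Baseline score. Appendix D does print a 0 box for all five locations, so sites may record 0 instead.
- SAP 4.1.4.2 foresees a blank Baseline IS at a location affected later. Its remedy imputes 0 at post-baseline time points, and only for time to minimal symptoms. It does not supply a Baseline value for the failure rule.
- Read literally, a new swelling at such a location does not meet the SAP criterion but does meet Appendix F's. The error runs one way: failures can be missed, not added.
- The number of blank Baseline scores is not in the documents.

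**2. Medication lists compared**
- In Appendix F but not in SAP 4.1.4.6: recombinant human C1 inhibitor.
- In SAP 4.1.4.6 but not in Appendix F: bradykinin receptor antagonists, analgesics, NSAIDs, and paracetamol within 45 minutes before dosing.
- In SAP 4.1.4.6 but not in Protocol 10.1.3: the paracetamol item only. SAP 7.4 records that the failure list was aligned with the disallowed-medication list.
- The lists are introduced by *including*, so an omission may just mean that a list is not exhaustive. That cannot reconcile Appendix F, which names recombinant C1 inhibitor, with Protocol 8.2.2, which excepts Ruconest.

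**3. Clock**

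Inputs:
- T is the time in minutes from start of infusion to the 4-hour VAS. Protocol 10.2.4.2 allows 240 ± 24, so T lies in [216, 264]; uniform spread is assumed.
- d is the lag in minutes from Baseline VAS to infusion. Protocol 10.2.3 and Appendix A note 2 put the VAS just before infusion; d of 1 and 5 is assumed.
- The SAP uses actual times.

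An attack whose persistent relief is first met at the 4-hour VAS changes class if T ≤ 240 and T + d > 240. The probability is d/48.

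| d | Late, from infusion | Late, from Baseline: (24 + d)/48 | Changed: d/48 |
|---|---|---|---|
| 1 | 24/48 = 50% | 25/48 = 52.1% | 2.1% |
| 5 | 24/48 = 50% | 29/48 = 60.4% | 10.4% |

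Other visits do not matter. The 2-hour window ends at 120 + 12 = 132 minutes, so a lag above 240 − 132 = 108 minutes would be needed. The 8-hour window (± 1 hour, Protocol 10.2.4.2) opens at 420 minutes, late on either clock.

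Expected change in the first-attack failure rate = s × d/48, where s is the share first relieved at the 4-hour VAS (assumed):

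| s | d = 1 | d = 5 |
|---|---|---|
| 1/20 | 0.1 points | 0.5 points |
| 2/20 | 0.2 | 1.0 |
| 4/20 | 0.4 | 2.1 |
| 8/20 | 0.8 | 4.2 |

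The largest entry is 8 × 5/48 = 0.83 child of 20. The Baseline clock can only add failures, the opposite direction to item 1. One child of 20 is 1/20 = 5 points.

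**The case against.** **The SAP repeats the protocol.** For the 4-hour limit this is right: SAP 4.1.4.6 reproduces Protocol 10.1.3. A reader might infer that the SAP moved the failure clock without saying so, but the documents do not support that. The conflict lies inside the protocol, between 10.1.3 and Appendix F. What the SAP changed is the origin of VAS and IS time to event. The relapse bullet ("Within 4 hours after beginning of treatment administration and after beginning of relief, the Overall VAS increases again") is a separate criterion, also taken from Protocol 10.1.3. It shows mixed clocks in one list but does not contradict the relief limit.

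**The lag is short, so nothing changes.** This stands in part: the expected effect is under one child even at the top of the range shown. A reader might go further and argue from earlier trials that almost no attack is first relieved at 4 hours. Protocol 9.3 does not settle that. Medians after rhC1INH in the two randomised trials, their extensions and the adolescents run from 37 to 122 minutes, and 122 minutes was the 50 U/kg arm of the 1205 randomised trial.

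**Second doses are reported anyway.** True. SAP 4.1.4.7 and 6.7.6 summarise them by attack, so the number of attacks that could be affected is visible. Whether they count as failures remains unresolved.

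**The new-location gap may be empty.** Possible, if sites marked 0 at unaffected locations. The documents do not say.

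**Conclusion.** The inconsistency is real and minor. The new-location rule comes first, because following the SAP literally can miss a failure that the protocol's definition counts. The medication passages contradict each other over a second Ruconest dose before relief. The effect of either cannot be computed from the documents; each reclassified child of 20 would move the first-attack rate by 5 points.

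The clock difference is worth 0.1 to 4.2 points in expectation. This rests on assumed lags of 1 to 5 minutes, uniform visit times, and 1 to 8 of 20 children first relieved at the 4-hour VAS. Attacks that already fail on another criterion would reduce it.

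A reader might infer that the study's main conclusion is in doubt. It is not: the primary objective is safety, therapeutic failure is exploratory and descriptive, and SAP 5.2 rules out formal hypothesis testing.

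**What to change.** - Define a new location as IS above 0 where Baseline IS was 0 or missing, as in Appendix F.
- Use start of infusion as the one time zero for VAS and IS time to event and for the 4-hour limit. Appendix F defines it so, Protocol 10.2.4.2 measures visit windows from it, and the SAP's TEQ and complete-resolution endpoints already count from dosing. Keep actual times.
- Reconcile the medication passages in Appendix F, Protocol 8.2.2, Protocol 10.1.3 and SAP 4.1.4.6, including whether a second Ruconest dose before relief counts and how the paracetamol item is treated. This review does not choose between them.

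No new data are needed. The SOP deviation form attached to the SAP says the analysis is final, so the cost is derivation code and reporting: re-derive Tables 14.2.1.5, 14.2.1.6 and 14.2.1.8 with the matching Kaplan-Meier figures and Figure 14.2.1.8, and check individual cases in Listing 16.2.6.1.4. SAP 7.5 sends changes after database lock to the clinical study report, so describe and justify them there.
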